## 7.3.4 Replacement of subjects

Patients that are not able to participate to the study will receive the standard of care, consisting of endoscopic dilations alone. Only 1 intralaesional administration of the study drug is given at the start of the experiment. Early drop-out of the study (before 6 months) will therefore not impact further standard care of the patient.

## 7.3.5 Restrictions and prohibitions for the subjects

- Patient need fasting for at least 8 hours prior to the gastroscopies
- Patients on anticoagulant medication need to interrupt the treatment according to the recommendations of the treating physician ([name] or [name])

### 7.3.6 Possible advantages and risks for the subjects

It is possible that participation to the study will result in less need for repeat dilations for a refractory upper GI stricture (unknown).

Every dilation carries the risk of perforation, even in the most experiences hands. No additional dilations are performed in light of the study. It is unknown whether local injection of the study drug augments the risks of perforation. Every patient is carefully monitored after dilation (standard of care). Upon clinical suspicion of perforation, a CT scan is performed for confirmation.

suspicion of perforation, a CT scan is performed for confirmation. In case of confirmed perforation, endoscopic stenting is immediately performed to bridge the defect, allowing healing of the defect. The stent can most of the time be removed after 6 weeks. In some case, endoscopic clipping is the treatment of choice to close the iatrogenic perforation. Surgical intervention is seldomly needed

Side effects of the study drug (XiapexR) are expected to be very limited, as the study drug does not enter the bloodstream in significant amounts and is rapidly degraded in the bloodstream by proteases. Local reactions (bleeding, swelling, inflammation) are theoretically possible. Like all foreign substances, Xiapex can induce allergic reactions but these seem to be very rare (only 1 case described in literature).

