# 6 Introduction

The main causes of benign gastrointestinal (GI) strictures are inflammatory (eg: reflux disease, eosinophilic esophagitis, Crohn's disease, caustic...) or iatrogenic (postirradiation, post endoscopic (sub)mucosal resection, post radiofrequency ablation, anastomotic...). Most strictures respond well to endoscopic balloon dilation. Nonetheless, more than one third of patients develop recurrent symptoms after dilation within the first year (1).

In some case, the stricture can be difficult to treat and require multiple dilation sessions to obtain long-term relief of dysphagia, eating difficulties or lower GI obstructive symptoms (2, 3). A refractory stricture is defined as a cicatricial or fibrotic narrowing luminal diameter resulting in clinical symptoms of a) dysphagia (esophageal strictures), b) gastric outlet obstruction (for strictures of the stomach, pylorus, duodenum of gastrojejunal anastomosis) or c) lower GI obstruction (abdominal distension and cramps, vomiting) with an inability to successfully remediate the anatomic problem to a sufficient diameter over 3 dilation sessions at two-week intervals (4). A recurrent stricture is defined as a cicatricial or fibrotic narrowing with an inability to maintain a satisfactory luminal diameter for four weeks (4). Several options (stenting, intralesional injection of corticosteroids, needle knife incision) have been proposed to manage these strictures, with a varying success rate (5). A significant proportion of patients will finally need self-bougienage or surgery (5).

In conclusion, the treatment of GI strictures remains a challenge for clinicians and there is an unmet need for novel approaches to manage the patients suffering from this condition in order to avoid repeated dilations and/or invasive surgery.

XiapexR is a locally injectable collagenase approved for the management of Dupuytren's and Peyronie's disease (6, 7). Xiapex is a mixture of two collagenases, enzymes produced by the bacterium *Clostridium histolyticum* that dismantle collagen. Approximately 24 hours after local injection, the collagen fibres have lost their

strength and can be easily broken by manipulation. This therapy has been a breakthrough in the management of Dupuytren's disease, avoiding surgery in the vast majority of patients (6).

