After local injection, the collagenases do not reach the bloodstream in significant amounts and are presumed to largely stay at the point of injection until they are broken down by proteases. As a result, side effects are uncommon and are most often injection site reactions including lymphadenopathy (swollen lymph nodes), itching, pain, oedema, and bleeding (for example in the form of bruises or ecchymoses). Allergic reactions are seen in less than 1% of patients (8).

XiapexR has been proposed as a promising treatment for refractory urethral strictures but has never been evaluated in refractory GI strictures (9).

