### 7.3.2 Inclusion criteria

The patient is 18-90 years old The patient suffers from a GI stricture The stricture is amenable for endoscopic dilation The patient has undergone at least 1 previous endoscopic dilation for the same stricture within the last 3 months The patient has signed the ICF

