## 8.2 Flowchart

- Between day -7 to day -1: Informed consent

- Day 0: Endoscopy, xiapex injection into the strictures (4 quadrants, 0.75ml or 0.25mg per quadrant)
- Day +1: Endoscopy, CRE balloon dilation 12mm to max 15mm
- Day +2 to month 2: clinical evaluation (by phone) every 2 weeks with a window of 3 days (see above for primary and secondary outcome measures)
- Month 2-month 6: Clinical evaluation (by phone) every 4 weeks with a window of 3 days (see above for primary and secondary outcome measures)

The expected total duration of the trial is 18 months.

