#### Serious Adverse Avent (SAE)

Any untoward medical occurrence that at any dose:

- results in death
- is life-threatening
- requires inpatient hospitalization or prolongation of existing hospitalization,
- results in persistent or significant disability/incapacity,
- or

- is a congenital anomaly/birth defect.

Note: Medical and scientific judgment should be exercised in deciding whether expedited reporting is appropriate in other situations, such as important medical events that may not be immediately life-threatening or result in death or hospitalization but may jeopardize the subject or may require intervention to prevent one of the outcomes listed in the definition above.

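### No rule clears one patient's Day +1 dilation before the next injection or holds enrolment after a perforation, although the perforation risk with the drug is stated to be unknown

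*Combined protocol and SAP*

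**What the plan says.** The Introduction (section 6) says that the product "has never been evaluated in refractory GI strictures". It gives the mechanism: "Approximately 24 hours after local injection, the collagen fibres have lost their" strength and break easily when manipulated. The flowchart in section 8.2 places the injection on Day 0 and the dilation at that 24-hour point: "Day +1: Endoscopy, CRE balloon dilation 12mm to max 15mm". Section 7.3.6 accepts that any dilation can perforate and says of the drug: "It is unknown whether local injection of the study drug augments the risks of perforation."

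The safeguards are these:

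- **Care of the patient (section 7.3.6).** Monitoring after dilation, CT on suspicion, then stenting or clipping.
- **Reporting (section 11).** An event that "requires inpatient hospitalization or prolongation of existing hospitalization" is an SAE. A note allows other important medical events to be expedited. The investigator reports an SAE within 2 working days of learning of it, and it goes on to the ethics committee. A SUSAR also goes to the competent authority, within 7 or 15 calendar days. For each adverse event, continuation or withdrawal is recorded.
- **Oversight (sections 13 and 16).** The principal investigator collects the data prospectively. The ethics committee receives progress reports, and an amendment may take effect without prior approval to remove an immediate hazard.

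Complication rate is a secondary outcome without a threshold (section 4), and the analysis is descriptive only (section 12.3). The available text sets no interval between patients and no perforation count that pauses injections.

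**The concern.** The dilation is deliberately timed to when the collagen has been weakened, so the open safety question bears on the step every patient undergoes the day after injection. Once injected, a patient is due for dilation the next day. If two patients are booked close together, the second can be injected before the first dilation has been done and observed. The 2 working days allowed for an SAE report can exceed the one day between injection and dilation, so reporting alone does not prevent this.

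The larger gap is at trial level. As written, injections may continue to the tenth patient after one perforation or after several, and the plan does not say when the events would be looked at together. At stake is how many further patients are exposed if the drug does raise the risk.

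**Working it through.** The plan gives no perforation rate, safety boundary or sample size calculation, so there is no figure of its own to reproduce. What follows sizes the two missing rules.

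**Inputs**

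- Patients treated: n = 10 (section 7.3.1).
- Accrual: not stated. Section 8.2 expects 18 months in total, with 6 months' follow-up, so 18 − 6 = about 12 months (T = 365 days).
- Clearance time: assumed g = 2 to 3 days from Day 0 (dilation on Day +1, then observation, whose length is not given).
- True perforation rate: assumed p = 2%, 5%, 10% and 20%.
- Arrivals: assumed random and uniform over T.

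**Hold.** Let X be binomial(10, p). A hold at the k-th perforation is reached with probability P(X ≥ k). If enrolment never resumes and every result is known before the next Day 0:

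- mean number treated, first-event hold = P(X ≥ 1)/p
- mean number treated, second-event hold = [P(X ≥ 1) + P(X ≥ 2)]/p
- patients spared = 10 − mean treated; perforations averted = p × patients spared

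Example at 5%: P(X ≥ 1) = 1 − 0.95^10 = 0.4013; treated 0.4013/0.05 = 8.03; spared 1.97; averted 0.05 × 1.97 = 0.10.

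| True rate | First event: reached | spared | averted | Second event: reached | spared | averted |
|---|---|---|---|---|---|---|
| 2% | 18% | 0.85 | 0.02 | 1.6% | 0.04 | 0.001 |
| 5% | 40% | 2.0 | 0.10 | 8.6% | 0.25 | 0.01 |
| 10% | 65% | 3.5 | 0.35 | 26% | 0.85 | 0.08 |
| 20% | 89% | 5.5 | 1.1 | 62% | 2.4 | 0.48 |

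The spared and averted figures are upper bounds. The proposal is a pause for review, after which enrolment may resume, and a late perforation may surface only at a scheduled call, after the next injection.

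**Clearance alone**

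1. Expected number of the 9 intervals shorter than g: 9 × [1 − (1 − g/T)^10] = 0.48 (g = 2) to 0.71 (g = 3).
2. Chance of at least one: 1 − (1 − 9g/T)^10 = 40% to 54%.
3. A short interval matters only if the earlier patient perforates. Multiplying line 1 by p gives the expected number injected before the preceding patient's perforation is known: 0.010 to 0.014 at 2%, 0.024 to 0.036 at 5%, 0.048 to 0.071 at 10%.
4. Multiplying by p again gives the perforations that clearance could avert: 0.0002 to 0.0003, 0.001 to 0.002, and 0.005 to 0.007. At 20% it is 0.48 × 0.04 = 0.02 to 0.71 × 0.04 = 0.03.

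If accrual took only 6 months, line 1 would be 0.94 to 1.37, and line 4 at 10% would be 0.009 to 0.014.

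**Waiting.** In a simulation of 400,000 trials over 12 months, a 2- to 3-day gap made 0.5 to 0.7 of 10 patients wait, by a mean of 1.0 to 1.6 days each. The last patient was delayed by a mean of 0.06 to 0.13 days. A wait over 7 days occurred in under 0.2% of trials.

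**Final report.** For 0 of 10 perforations, the exact two-sided 95% upper limit is 1 − 0.025^(1/10) = 0.308, about 31%.

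**The case against.** The case for leaving the plan alone is fair in four respects.

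- **Spacing.** A reader might infer from the 40% to 54% chance of a short interval that about half of such trials would expose someone to avoidable harm. The plan does not support that. The figure counts scheduling overlaps, and the clearance time behind it is assumed: with a 1-day gap it falls to 22%. The harm that clearance alone prevents is a tiny fraction of one event.
- **Oversight.** A reader might also infer that nobody outside the study would see a perforation. Sections 11, 13 and 16 say otherwise. In a 10-patient study the principal investigator would learn of each event, SAE and SUSAR reports reach the ethics committee and, for SUSARs, the competent authority, and the immediate-hazard clause allows fast action. These provisions narrow the gap. They do not close it, because each is discretionary and none sets a trigger.
- **Size of benefit.** The hold figures assume permanent stopping, and at true rates of 2% to 5% even the first-event hold averts at most 0.02 to 0.10 perforations. This stands.
- **Risk itself.** The product is licensed for other uses, and dilation carries a perforation risk without it. The documents do not show that the drug raises that risk; they say that it is unknown. A hold may therefore follow an event that owes nothing to the drug.

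What remains is that the plan names the risk as unknown, permits a halt, and fixes no point at which one must be considered.

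**Conclusion.** The concern holds as a modest safety addition that should be made. The protocol neither links one patient's Day +1 result to the next injection nor pauses enrolment after a perforation. The value lies mainly in the hold and grows with the true rate: small at 2%, and at most 5.5 patients spared and 1.1 perforations averted at 20%. Clearance adds well under 0.01 averted perforations at rates up to 10% over 12 months. It is needed because the hold works as calculated only if each result is known before the next Day 0.

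The size rests on assumed perforation rates, random arrivals, about 12 months' accrual and a 2- to 3-day clearance. The absence of the two rules rests on the text alone. A first-event hold is preferable here: waiting for a second event cuts pauses at a 2% rate from 18% to 1.6% of trials, but at 10% it spares 0.85 patients instead of 3.5.

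**What to change.** **Section 8.2.** Allow the next Day 0 only after the previous patient's Day +1 dilation and observation are recorded as free of suspected perforation, or a suspicion has been excluded.

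**Section 11.** Hold new injections at the first confirmed perforation, including a late one found at a scheduled call, until the sponsor and the ethics committee have reviewed it. State two consequences:

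- A patient already injected when a hold starts is managed by the treating endoscopist under standard care.
- If the hold outlasts the consent window ("Between day -7 to day -1: Informed consent") or the eligibility window ("The patient has undergone at least 1 previous endoscopic dilation for the same stricture within the last 3 months"), consent is renewed and eligibility rechecked.

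**Section 12.3.** Report the perforation rate with its exact (Clopper-Pearson) interval, so that 0 of 10 is not read as proof of safety.

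**Cost.** A short protocol amendment, with no extra patients or procedures. Clearance costs the 1- to 2-day waits shown above, and booking Day 0 before consent is signed would keep the consent window intact in nearly all cases. The hold costs a review pause after a chance event, in about 18% of trials if the true rate is 2%. The length of that review is not known, so the delay it causes cannot be calculated from the documents.

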# 8 Procedures

## 8.1 Procedures

After informed consent, patients with an a refractory upper GI stricture will receive a first esophagogastroscopy or ileocolonoscopy with local injection of XiapexR injection into the stricture prior to dilatation. One vial (0.9mg) xiapex in 3ml dissolvent (also provided by the company) will be divided over 4 quadrants within the fibrotic stricture. After 24 hours, a second esophagogastroscopy or ileocolonoscopy will be performed to perform balloon dilation of the stricture 12-15mm (standard of care). The historical cohort will not undergo any procedures, but their patient file will be reviewed to gain outcome data. ICF will be obtained if the patient is still in follow-up at our department.

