# Part I : Trial related part of the protocol

# 1 Title of the trial

Local injection of collagenase clostridium histolyticum (XiapexR) for refractory gastrointestinal strictures: an open-label pilot study.

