# 4 End point(s) and timepoint(s) of evaluation

### Primary outcome measure:

Number of repeat dilations that are required over a timespan of 6 months.

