### Secondary outcome measures:

1) time to first repeat dilation

- 2) complication rate.
- 3) For upper gastrointestinal strictures only: Dysphagia/gastric outlet obstruction

score (0:, able to eat normal diet; 1: moderate passage: able to eat some solid foods;

2: poor passage: able to eat semi-solid foods only; 3: very poor passage: able to drink liquids only; 4: no oral intake possible

4) For lower gastrointestinal strictures only: (Ileo)colorectal obstruction scoring system (0, requiring continuous decompression; 1, no oral intake; 2, liquid or enteral nutrition; 3, oral intake of soft solids, low-residue diet, or full diet with symptoms of stricture\*; and 4, oral intake of soft solids, low-residue diet, or full diet without symptoms of stricture\*. Symptoms of stricture include abdominal pain/cramps, abdominal distension, nausea, vomiting, constipation, and diarrhea which are related to gastrointestinal transit).

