## 7.3 The subjects

### 7.3.1 Number of subjects

Active group: 10 patients presenting with refractory GI strictures.

Control group: A historical cohort that consists of 40 consecutive patients that received an endoscopic balloon dilation 12-15mm for a refractory GI stricture at our centre.

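### Sections 8.1 and 7.3.6 describe upper GI strictures only while the rest of the protocol includes lower ones, and the primary comparison has no split or matching by stricture site

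*Combined protocol and SAP*

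**What the plan says.** The population is described in two ways.

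- **Whole GI tract.** The title (section 1) reads "for refractory gastrointestinal strictures: an open-label pilot study". The inclusion criterion in 7.3.2 is "The patient suffers from a GI stricture", with no site limit. Section 7.3.1 describes the 10 active patients as having refractory GI strictures, and the control group as "A historical cohort that consists of 40 consecutive patients that received an endoscopic balloon dilation 12-15mm for a refractory GI stricture at our centre". Section 4 has a score that applies to lower strictures alone: "For lower gastrointestinal strictures only: (Ileo)colorectal obstruction scoring system".
- **Upper GI only.** Section 8.1 states that "patients with an a refractory upper GI stricture will receive a first esophagogastroscopy or ileocolonoscopy", so one sentence names an upper population and a lower-tract procedure. Section 7.3.6 gives the hoped-for benefit as "less need for repeat dilations for a refractory upper GI stricture (unknown". Section 7.3.5 mentions preparation for one procedure only: "Patient need fasting for at least 8 hours prior to the gastroscopies".

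The primary outcome in section 4 is "Number of repeat dilations that are required over a timespan of 6 months", with no division by site. Section 12.3 plans a descriptive comparison with the historical group and mentions no matching, stratification or reporting by site. Section 9 confirms that there is no randomisation.

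**The concern.** There are two linked problems.

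The first is the conflict in wording. A reader of 8.1 and 7.3.6 would take the treated population to be upper strictures. A reader of 7.3.2 and secondary outcome 4 would not. No passage settles it.

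The second matters more for the result. The protocol treats upper and lower strictures as clinically different: section 6 gives them different presenting symptoms, and section 4 gives them separate scores that run in opposite directions (0 is the best value for upper strictures and the worst for lower). Yet the primary count has no such separation, and the comparator is a single consecutive cohort with whatever mix of sites the centre happened to see. The objective in section 3 is whether injection followed by dilation improves outcome over dilation alone. An overall difference in counts would be read as the answer, although part of it could come from a different share of upper strictures in the two groups.

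**Working it through.** The plan has no sample size, power or effect figure (12.1), so there is nothing to reproduce. The check is a comparison of passages followed by a bias formula.

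**1. Passages side by side**

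| Section | Population implied |
|---|---|
| 1 Title | GI tract, no limit |
| 4 Secondary outcome 4 | Lower strictures expected |
| 7.3.1 Active and control groups | GI tract, no limit |
| 7.3.2 Inclusion | Any GI stricture |
| 7.3.6 Benefit statement | Upper only |
| 8.1 Procedures | Upper in wording, lower by procedure |

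The conflict is confirmed. Most of these passages, and half of the 8.1 sentence, include lower strictures.

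**2. Bias from site mix when the drug has no effect**

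Let pA and pC be the upper shares in the active and control groups, and mU and mL the mean 6-month counts for upper and lower strictures.

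- Active mean = pA·mU + (1 − pA)·mL
- Control mean = pC·mU + (1 − pC)·mL
- Difference = (pA − pC) × (mU − mL)

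The difference is zero if pA = pC or mU = mL.

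None of the four inputs is in the documents. The values below are assumptions, chosen only to show how the formula behaves:

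| mU, mL | pA, pC | Active mean | Control mean | Difference |
|---|---|---|---|---|
| 4, 2 | 0.5, 0.8 | 3.0 | 3.6 | −0.6 (−17%) |
| 4, 2 | 0.8, 0.5 | 3.6 | 3.0 | +0.6 (+20%) |
| 3, 2 | 0.5, 0.8 | 2.5 | 2.8 | −0.3 (−11%) |
| 3, 2 | 0.8, 0.5 | 2.8 | 2.5 | +0.3 (+12%) |
| 2, 2 | any | 2.0 | 2.0 | 0 |

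For example, 0.5 × 4 + 0.5 × 2 = 3.0, 0.8 × 4 + 0.2 × 2 = 3.6, and (0.5 − 0.8) × (4 − 2) = −0.6.

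**3. How large a share gap chance alone would give**

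The inputs from 7.3.1 are 10 active and 40 control patients. Assume that both groups are drawn from one common mix with true upper share p. The probabilities come from the product of two exact binomials, n = 10 and n = 40. The standard deviation of the gap is √[p(1 − p)(1/10 + 1/40)].

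| p | SD of gap | P(gap ≥ 20 points) | P(≥ 30) | P(≥ 40) |
|---|---|---|---|---|
| 0.5 | 0.18 | 0.29 | 0.10 | 0.027 |
| 0.7 | 0.16 | 0.25 | 0.07 | 0.015 |
| 0.8 | 0.14 | 0.18 | 0.04 | 0.006 |

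A 20-point gap is therefore quite likely even with no systematic difference, and a 40-point gap is rare. At 20 points, the false difference would be 0.2 × 1 = 0.2 dilations if the sites differed by one dilation on average, and 0.2 × 2 = 0.4 if they differed by two.

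**4. After the fix**

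Within one site category the upper share is the same in both groups (1 or 0), so (pA − pC) = 0 and this term vanishes whatever mU and mL are.

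**The case against.** The best defence is that the intended population is clear. Eligibility is set in 7.3.2, secondary outcome 4 exists only for lower strictures, and 8.1 provides for ileocolonoscopy at both the injection and the dilation visit. On that view, the word upper in 8.1 and 7.3.6 is leftover wording. This largely stands: taken alone, the conflict is close to clerical. A reader might infer from 8.1 that only upper strictures will be enrolled, leaving secondary outcome 4 without active patients. The rest of the protocol, including 8.1's own procedures, does not support that.

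A reader might also infer that the plan commits to a pooled analysis. It does not say so. Section 12.3 names no estimator; the absence of a split is inferred from a single primary count, a single cohort and silence on site.

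A third tempting inference is that the result will be badly distorted. The documents contain no rates by site and no mix, so neither size nor direction can be derived, and step 3 shows that very large gaps are unlikely by chance.

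It is also fair that this is an openly declared pilot with descriptive analysis, and that an upper/lower split leaves cause of stricture and finer location mixed. But descriptive reporting avoids p-values without removing confounding, and the comparison with dilation alone remains the stated objective. That other differences remain is no reason to leave this one unshown, since the protocol already uses the distinction for its scores.

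**Conclusion.** The point holds in a limited form. The wording conflict is certain and minor. The substantive gap is that the primary count is compared with an unmatched cohort of any GI site, without randomisation and with no planned display by site. The crude difference can therefore partly reflect site mix. It cannot be said that it does. This depends on two conditions that the documents leave open: that repeat-dilation rates differ between upper and lower strictures, and that the groups differ in their upper share. The second is plausible even under a common mix, with probability about 0.18-0.29 of a gap of at least 20 points for true upper shares of 50-80%. The first is an assumption. The change is worth making because it costs little and removes this source of ambiguity.

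**What to change.** 1. Reconcile the population wording in 8.1 and 7.3.6 with sections 1, 4, 7.3.1 and 7.3.2. Section 7.3.5, which names gastroscopies only, should be read against the ileocolonoscopy in 8.1 at the same time; what preparation is right is for the clinical team.
2. If lower strictures are eligible, state in 12.3 that stricture site will be tabulated in both groups, and that the number of repeat dilations over 6 months will be shown separately for upper and lower strictures, each against controls of the same site. Any overall figure should appear beside the site mix of both groups. Standardising the control mean to the active group's mix is optional; with 10 active patients the weights would be rough.
3. If the sponsor confirms upper strictures only, restrict the controls to upper strictures, remove secondary outcome 4 and bring the other passages into line.

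The cost is a few sentences of protocol text. No patients, visits or procedures are added. Site should be evident from the endoscopy and from the control files, which 8.1 already plans to review, although the documents do not state that every file records it. No power is lost, since none was calculated. The downside is that one site category may hold very few of the 10 active patients; those results should be shown descriptively as such.

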# 7 The present study

## 7.1 Study design

Proof of concept open pilot study with a historical control cohort.

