## 12.3 Statistical analysis

This is a proof of concept open label study that will compare outcome data with a historical control group. Only descriptive analyses will be performed, the sample size will be too low for any meaningful statistical analysis.

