# 13 Quality control and quality assurance

The principal investigator will prospectively collect the pseudonymized data and ensure the quality of the study procedures and study data (see also section 17 up to 21).

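### The historical control outcomes come from a file review with no set timing, lock or counting rule, so the comparator can be settled after active results are seen

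*Combined protocol and SAP*

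**What the plan says.** Section 7.1 gives the design as "Proof of concept open pilot study with a historical control cohort", and Section 3 frames the objective as a comparison with dilation alone. Section 7.3.1 defines the groups: "Active group: 10 patients presenting with refractory GI strictures", and for the controls "A historical cohort that consists of 40 consecutive patients that received an endoscopic balloon dilation 12-15mm for a refractory GI stricture at our centre".

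Control outcomes are obtained retrospectively. Section 8.1 states: "The historical cohort will not undergo any procedures, but their patient file will be reviewed to gain outcome data". On consent it adds: "ICF will be obtained if the patient is still in follow-up at our department". The primary outcome in Section 4 is "Number of repeat dilations that are required over a timespan of 6 months". Section 12.3 says the study "will compare outcome data with a historical control group" and limits the analysis to description.

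For the active group, Section 8.2 schedules telephone evaluations every two weeks up to month 2 and every four weeks from then to month 6. Section 9 treats randomisation and blinding as not applicable. On data collection, Section 13 says: "The principal investigator will prospectively collect the pseudonymized data and ensure the quality of the study procedures and study data".

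**The concern.** In a randomised trial the comparator is fixed by allocation and its outcomes build up alongside those of the treated group. Here the control events have already happened, and turning files into data takes judgement: whether a past stricture was refractory, which dilation starts the six-month clock, whether a later dilation was required, and whether a finding is a complication. Active counts become known call by call. If the control review runs during or after that follow-up, each judgement can be made, even in good faith, by someone who knows which answer would favour the injection.

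At stake is the comparison that Section 3 sets as the objective. With no test, margin or decision rule to temper it, a descriptive contrast is only as credible as the way its comparator was built.

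**Working it through.** **1. Is there a safeguard anywhere?** The sections that could hold one were read side by side.
- 7.3.1 gives the number of controls and the word consecutive, but no dates.
- 8.1 provides for the file review, but gives no start, finish, reviewer or extraction rule.
- 9 provides no blinding, and none for file review.
- 12.3 plans the comparison, with no lock and no order of work.
- 13 gives the principal investigator data collection and quality, with no separation between active results and control extraction.

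None sets an order, a lock or a reviewer unaware of active results.

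**2. What does the consecutive rule settle?** It rules out choosing individuals. Four things stay open:
- *Window.* There is no start date, end date or counting direction for the 40.
- *Eligibility.* Section 6 defines refractory as failure over three sessions at two-week intervals. Section 7.3.2 asks only for at least one earlier dilation within three months. Section 7.3.1 uses the word refractory for both groups without saying which standard applies to old files.
- *Index dilation.* Active patients have a dated study dilation (day +1 in Section 8.2). A control may have had several dilations, and none is named as the start.
- *Counting.* Section 4 does not say what makes a dilation required, or whether planned serial dilations count.

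**3. How large could the effect be?** The plan has no figure to reproduce: Section 12.1 gives no sample size calculation, and no control mean, spread or pool size appears. What follows is illustration on assumed inputs.

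*Choice of window.* Assume no drug effect, a true mean of 2 to 4 repeat dilations in six months, and counts that are Poisson or negative binomial with dispersion parameter 2 or 1. From a pool of M eligible patients in date order, take the run of 40 with the highest mean. Shift = expected highest mean of any 40 in a row, minus the true mean (20,000 simulated pools per scenario).

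| Pool M | Lowest shift (mean 2, Poisson) | Highest shift (mean 4, dispersion 1) |
|---|---|---|
| 40 | 0 | 0 |
| 60 | 0.15 | 0.46 |
| 80 | 0.22 | 0.69 |
| 120 | 0.31 | 0.98 |

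For scale, the standard error of a 10 versus 40 difference is √[variance × (1/10 + 1/40)] = √(0.125 × variance).
- Mean 2, Poisson: variance 2, standard error √0.25 = 0.50.
- Mean 4, dispersion 1: variance 4 + 4²/1 = 20, standard error √2.5 = 1.58.

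The shift is therefore about 0.3 standard errors with a pool of 60 (0.15/0.50; 0.46/1.58) and about 0.6 with a pool of 120 (0.31/0.50; 0.98/1.58).

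*Choice of counting rule.* If a fraction q of recorded control dilations is ambiguous, counting or omitting them moves the control mean by q × mean. This runs from 0.10 × 2 = 0.2 to 0.30 × 4 = 1.2. It shifts the contrast by that amount only if the active group is not counted by the same rule. With no drug effect and one rule applied alike to both groups, the two means would be expected to move together.

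**The case against.** The strongest reply is that this is a ten-patient proof-of-concept study limited to description, that the consecutive rule already constrains the controls, and that silence on the order of work is not evidence of misuse. Much of that stands. No threshold or test can be flipped, and on the assumptions above the window shift is smaller than the sampling error of the comparison. Sampling error, however, has no preferred direction, whereas a choice made with results in view does.

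Four stronger readings are tempting, and the documents do not support them.
- *Any 40 patients could be picked.* Section 7.3.1 requires consecutive patients, so only the window and the eligibility standard are open. The past tense there may even mean that the cohort was already identified, though this is not conclusive.
- *The principal investigator or trial team reviews the files.* Section 8.1 names no reviewer. Section 13 speaks of prospective collection, which most naturally describes the active group. The gap exists whoever does the review.
- *The bias has a known size.* One shortcut is the expected maximum of K independent control means. With an assumed SD of 2 the standard error is 2/√40 = 0.316, giving 0.564 × 0.316 = 0.18 for K = 2 and 1.163 × 0.316 = 0.37 for K = 5. Independence would need 2 × 40 = 80 to 5 × 40 = 200 different patients, which the documents do not establish. Nor does it model which dilations count within the same 40 files.
- *A lock would remove the problem at no cost.* The controls are from the same centre, so staff may already know their outcomes, and consent from those still in follow-up takes time.

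**Conclusion.** The concern holds as an avoidable opportunity for bias; nothing shows that bias occurred. The plan lets the control window, the eligibility standard, the index dilation and the counting rule be settled after active results are seen. The counting of dilations is the better supported part, because the consecutive rule does nothing to limit it.

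The size cannot be derived from the documents. It is zero if only 40 eligible patients exist and the counting rule is unambiguous. Otherwise it depends on pool size, mean and spread, all of which are assumed in the illustrations. The consequence falls on the credibility of the comparison with dilation alone. A reader might infer an inflated type I error rate, but no hypothesis test is planned.

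**What to change.** In Sections 8.1 and 12.3, first write the rules:
- the calendar window and counting direction for the 40 consecutive controls;
- one eligibility rule that matches the active group, with Sections 6 and 7.3.2 reconciled;
- the index dilation, and the rule for which repeat dilations count, the same in both groups.

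Then abstract the control data and lock them with a recorded date. Preferably this is done before the first active follow-up, and at the latest before any active six-month outcome is tabulated. Alternatively, have existing staff who are unaware of active results do the extraction. Log later corrections with a date and reason, and report the results with and without them.

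The rules must come before the lock, since a lock alone would freeze undefined choices. The cost is some scheduling effort, including control consent where required, which is why the earlier deadline is a preference. No extra patients or procedures are needed. The change reduces bias but does not remove it: staff may already know control outcomes, and active follow-up stays unblinded.
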